3.5 Interim Analysis and Data Review

As noted in Section 3.3, during the dose optimization phase, the ORR for each dose optimization cohort will be reviewed when 5 patients are determined to be evaluable. If no response of CR or PR has been observed in the cohort then enrolment in that cohort will be discontinued. Evaluation of response in this analysis will be based on Investigator assessments.

In addition, at the conclusion of the Dose Optimization Phase, all available data will be reviewed and an optimal dose for the Expansion Phase will be selected. In addition to recommending an optimal dose, the Expansion Phase may also involve modifications of the study patient population, other aspects of entry criteria, and the inclusion of patients from geographic regions outside the US; any such changes will be documented in an amendment to the protocol. The Sponsor study team, in collaboration with the Investigators, will make the determination of duvelisib dose for the Expansion Phase of the study based on the totality of available safety and activity data. This evaluation does not constitute an interim analysis.

During the expansion phase, two assessments of ORR will be conducted. The first will be a preliminary assessment of ORR after approximately 15 subjects have had an initial assessment of response by the investigator. During this assessment, the data from the expansion phase will be reviewed in the context of data from the dose optimization phase.

The second assessment will occur after 40 patients have been followed for a minimum of 4 months from the last patient's first dose and assessed for response by the IRC. At that time, enrollment in the Expansion Phase may be held if ORR is less than 20%. The efficacy data (including durability of response) will be reviewed in combination with safety and PK and upon review, the study may be fully stopped for futility.

- Additional interim analyses will be used for planning purposes, FDA submission and discussion and possible publication of early efficacy and safety results. The final analysis of the study will be completed and submitted to health authorities and published as appropriate. The approximate timing of these interim analyses are when: At least 75 of expansion phase patients have been followed for a minimum of 6 months from the last patient's first dose and assessed for response by the IRC.

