4.1 General Methods

Summary statistics will be presented by treatment group, unless stated otherwise.

Unless otherwise specified, descriptive statistics for continuous data will include the number of subjects with data to be summarized (n), mean, standard deviation, 25% quartile, median, 75% quartile, and minimum and maximum. The same number of decimal places as in the raw data will be presented when reporting the minimum and maximum, one more decimal place than the raw data will be presented when reporting mean and median, and 2 more decimal places than the raw data will be presented when reporting standard deviation.

Descriptive statistics for categorical/qualitative data will include frequency counts and percentages. The total number of subjects in the treatment group will be used as the denominator for percent calculations, unless stated otherwise. All percentages will be presented with one decimal, unless otherwise specified. Percentages equal to 100 will be presented as 100, and percentages will not be presented for zero frequencies.

Descriptive statistics associated with time-to-event analyses will include the number of events, the number of subjects censored, 25% quartile, median, 75% quartile, and 95% confidence interval for median. These statistics will be presented for all time-to-event analyses, unless stated otherwise.

Listings will be provided for selected endpoints.

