5.2.2 Analyses of Secondary and Exploratory Efficacy Endpoints

5.2.2.1 Duration of Response

Duration of response will be analyzed both for patients with ORR (CR or PR) and for patients with CR.

- Main DOR Analysis: DOR will only be calculated for those patients with a CR or PR from time to first response to PD or death (if death occurs prior to PD). Patients who withdraw from the study for any reason prior to PD and patients who have ongoing response at the time of the data cut will be censored at the date of their last response assessment.
- Duration of complete response (DOCR): DOCR is calculated from the time of first CR and only includes patients who had at least one CR response. It is otherwise defined the same as the Main DOR endpoint.

Estimates of the 25th percentile, median, and 75th percentiles will be for each of these DOR endpoints will be presented using the Kaplan-Meier method. A 2-sided 95% confidence interval for median DOR will be provided by using the Brookmeyer-Crowley method. Kaplan-Meier plots will be provided.

In addition, the number and percent of patients with duration of response of at least 3 months, 6 months and 12 months will be tabulated.

A summary of time to first response will also be presented in patients who achieved CR or PR and in patients who achieved CR.

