5.2.2.3 Analysis of PFS

For the PFS analyses, censoring of PFS will be performed as detailed in Table 2. Note that progression may be documented based on scheduled or unscheduled disease status assessment, and that unscheduled disease status assessments will be included in calculating the gap between adequate disease status assessments.

PFS will be estimated for each cohort using the Kaplan-Meier method. PFS will be plotted by using the Kaplan-Meier method. Number of patients with events, type of events (progression or death), number of patients censored, number of patients for each reason of censoring, Kaplan-Meier estimates and 95% confidence intervals for the 25th percentile, median, and 75th percentile for PFS will be presented. A 2-sided 95% confidence interval for median PFS will be provided by using the Brookmeyer-Crowley method. Probabilities of remaining alive and progression free at selected time points may also be presented.

PFS analysis will be repeated for the subset of enrolled Japanese patients and for each of the prognostic factors described in section 4.5.2

Situation	Date of Event or Censoring	Outcome
No adequate baseline disease status assessment	Date of randomization + 1 day	Censored
No adequate post-baseline disease status assessment unless death occurs prior to first scheduled post-baseline assessment	Date of randomization + 1 day	Censored

Table 2: Primary PFS Censoring/Event Rule

No documented progression or death	Date of last adequate disease status assessment	Censored
Documented progression with ≤1 missing scheduled disease status assessment before progression	Date of the earliest assessment that results in a finding of unequivocal progression	Event
Death before progression being documented with ≤1 missing scheduled disease status assessment before death	Date of death	Event
Documented progression or death following a gap between adequate disease status assessments equivalent to 2 missed visits	Date of last adequate disease status assessment before the gap	Censored
New anticancer treatment or procedure started before documented progression or death.	Date of last adequate disease status assessment prior to start of new anticancer therapy	Censored

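### The SAP's table of responses lasting at least 3, 6 and 12 months names no denominator and no rule for censored responders; read as a simple count, it gives only a lower bound

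*SAP*

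**What the plan says.** SAP 5.2.2.1 estimates DOR, and the duration of complete response (DOCR), by Kaplan-Meier. The outputs are quartiles and the following: "A 2-sided 95% confidence interval for median DOR will be provided by using the Brookmeyer-Crowley method. Kaplan-Meier plots will be provided". The patients censored are "Patients who withdraw from the study for any reason prior to PD and patients who have ongoing response at the time of the data cut", and they "will be censored at the date of their last response assessment". As a further item, "the number and percent of patients with duration of response of at least 3 months, 6 months and 12 months will be tabulated". That sentence gives no denominator, no estimator and no rule for a response censored before the landmark.

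Two other places bear on how to read it. SAP 4.1 sets a general default: "The total number of subjects in the treatment group will be used as the denominator for percent calculations, unless stated otherwise". For PFS, SAP 5.2.2.3 mentions landmark probabilities, though only as an option: "Probabilities of remaining alive and progression free at selected time points may also be presented". DOR has no matching sentence.

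Follow-up is described in SAP 3.3 and 3.5. One interim look occurs when "At least 75 of expansion phase patients have been followed for a minimum of 6 months", counted from the last patient's first dose. Another covers the 101 patients enrolled before protocol version 7.0, with at least 6 months after the last patient's first scheduled response assessment. The final analysis is triggered by evaluation of the primary endpoint, with no minimum DOR follow-up stated.

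**The concern.** A number and percentage, listed as an extra after the Kaplan-Meier outputs, reads most naturally as a count. A responder still in response but censored at month 5 is then not among those reaching 6 months, although nothing shows that the response ended. The percentage mixes how long responses last with how long patients have been watched, and the mixing is worst at 12 months.

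This is a single-arm trial, so the durability of responses is central to interpreting the ORR. SAP 3.5 says the additional interim analyses may serve discussion with FDA, a submission and early publication. A 12-month percentage well below the Kaplan-Meier curve in the same report would confuse its readers. With the denominator unstated, they also could not tell whether the figure describes responders or all treated patients.

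**Working it through.** The plan gives no landmark DOR figure, so there is none to reproduce.

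**Inputs from the documents.** Scans every 2 cycles of 28 days, so every 56 days or 1.84 months (SAP 3.1.2). Censoring at the last response assessment (SAP 5.2.2.1). Follow-up minimums from SAP 3.3 and 3.5. For illustration, 100 patients at the design ORR of 40%, so 40 responders (SAP 3.3).

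**Assumed, because the documents give no values.** Exponential DOR with median 6, 9 or 12 months; follow-up after response uniform over 12–24, 6–24 or 0–24 months; withdrawal either none or exponential with mean 36 months.

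**1. What the planned looks cover.** At the 75-patient look the last patient has 6 months from first dose. The first scheduled scan comes 1.84 months after that dose, which leaves 6 − 1.84 = 4.16 months. The 6-month landmark is therefore not covered for every responder. At the 101-patient look the guarantee is 6 months after the first scheduled assessment, so 12 months is not covered. Scans after a first response fall at 1.84, 3.68, 5.52, 7.36, 9.20, 11.04 and 12.88 months. A patient still in response with exactly 6 months of follow-up is censored at 5.52 and misses the 6-month count.

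**2. Direction.** Let T be the true duration and C the censoring time. The count divided by the number of responders estimates P(T ≥ L and C ≥ L), which cannot exceed P(T ≥ L). The same holds in any sample: the fraction still under observation falls with every event and every censoring, while the Kaplan-Meier estimate falls only with events. The two agree when nobody is censored before L.

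**3. Size at 12 months, no withdrawal.** On the scan grid, a response is seen to last 12 months if the true duration exceeds 11.04 months, and the patient is observed that long if follow-up reaches 12.88 months.
- Landmark probability = 0.5^(11.04/median) = 27.9%, 42.7%, 52.9% for medians 6, 9, 12.
- Chance of being observed that long: (24 − 12.88)/12 = 0.927 for 12–24 months; (24 − 12.88)/18 = 0.618 for 6–24; (24 − 12.88)/24 = 0.463 for 0–24.
- The count percentage is the product of the two. For median 12 it is 49.0%, 32.7% and 24.5% respectively.

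A simulation of 40 responders, 4,000 runs per scenario, agrees. Entries are count % against Kaplan-Meier %, among responders:

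| Landmark | Follow-up after response | Median 6 | Median 9 | Median 12 |
|---|---|---|---|---|
| 3 months | 6–24 months | 81 / 81 | 87 / 87 | 90 / 90 |
| 3 months | 0–24 months | 69 / 81 | 74 / 87 | 76 / 90 |
| 6 months | 12–24 months | 53 / 53 | 66 / 66 | 73 / 73 |
| 6 months | 6–24 months | 49 / 53 | 61 / 65 | 67 / 73 |
| 6 months | 0–24 months | 37 / 53 | 45 / 65 | 50 / 73 |
| 12 months | 12–24 months | 26 / 28 | 40 / 43 | 49 / 53 |
| 12 months | 6–24 months | 17 / 28 | 27 / 43 | 33 / 53 |
| 12 months | 0–24 months | 13 / 28 | 20 / 43 | 25 / 53 |

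From unrounded values, the 12-month shortfalls run from 27.8 − 25.8 = 2.0 to 52.8 − 49.0 = 3.8 points (12–24 months), 27.9 − 17.2 = 10.7 to 52.9 − 32.8 = 20.1 points (6–24), and 28.0 − 13.0 = 15.0 to 52.8 − 24.5 = 28.3 points (0–24).

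**4. Adding withdrawal.** With the assumed withdrawal, the 12-month shortfall for 12–24 months of follow-up becomes 27.8 − 18.0 = 9.8 to 52.8 − 34.1 = 18.7 points. The largest gap is 52.9 − 17.2 = 35.7 points, with no minimum follow-up and median 12.

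**5. Denominator.** Suppose 15 patients reach a landmark. That is 15/40 = 37.5% of responders but 15/100 = 15% of treated patients, and only the first can be set beside a DOR curve.

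**The case against.** A reader might infer that the SAP prescribes a crude proportion of responders in which everyone censored early counts as a failure. It does not say so. The text is silent on censored responders; leaving them out, or using Kaplan-Meier, is not ruled out. Nor are responders named as the base. DOR exists only for patients with CR or PR, which makes responders a natural choice, but the sentence does not override the SAP 4.1 default. The count is an inference, though the most natural one.

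A reader might also infer that the trial's durability result is understated. That is too broad. The main DOR and DOCR analyses are Kaplan-Meier and allow for censoring, and landmark values can be read from the planned plots. Numbers of events and censored patients (SAP 4.1), responders' follow-up from first response (SAP 5.1.1) and swimmer's plots (SAP 5.2.1.1) will show how mature the data are. No test or decision rule uses this table, and a lower bound cannot flatter the drug.

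Thirdly, the large gaps might be taken as a forecast of the final report. Short follow-up is a feature of the interim looks. Protocol version 7.0 is dated July 2021 and the final SAP August 2023, so many responders may have been followed past 12 months at the final cut. The cut date is not given, however, and withdrawals would still leave a gap.

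All of this limits the point but does not remove it. The percentage remains undefined as written, and the likeliest reading is biased downward.

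**Conclusion.** The point stands as a gap in specification with a predictable direction, confined to one supplementary table. Read as a count among responders, the percentage cannot exceed the Kaplan-Meier estimate; on the all-treated default it measures something else and is smaller still.

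The size rests on the assumed medians, follow-up patterns and withdrawal. Without withdrawal it runs from nothing, where every responder is observed past the landmark, to about 28 points at 12 months with no minimum follow-up. If the final cut gives every responder at least 12 months and few withdraw, the table would be nearly right. The documents guarantee neither condition.

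**What to change.** Replace the landmark sentence in SAP 5.2.2.1 with a plan to present, among responders, the Kaplan-Meier probability of remaining in response at 3, 6 and 12 months, with 95% CI and number at risk. Do this for DOR, and for DOCR among patients with CR. If the counts are kept, label them as observed duration, name the denominator, and show how many responders were censored before each landmark.

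The cost is one SAP sentence and slightly more output, from Kaplan-Meier fits already planned. Intervals will be wide where few responders remain at risk, which is an honest reflection of the data. Kaplan-Meier does not remove bias if early censoring is related to prognosis, so the censored numbers are worth showing in either case.

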5.2.2.2 Disease Control Rate

The proportion of patients demonstrating DCR (defined as patients with best overall response of CR or PR or with best overall response of SD sustained for at least 8 weeks) will also be presented along with 2-sided confidence intervals.

5.2.2.3 Analysis of PFS

For the PFS analyses, censoring of PFS will be performed as detailed in Table 2. Note that progression may be documented based on scheduled or unscheduled disease status assessment, and that unscheduled disease status assessments will be included in calculating the gap between adequate disease status assessments.

PFS will be estimated for each cohort using the Kaplan-Meier method. PFS will be plotted by using the Kaplan-Meier method. Number of patients with events, type of events (progression or death), number of patients censored, number of patients for each reason of censoring, Kaplan-Meier estimates and 95% confidence intervals for the 25th percentile, median, and 75th percentile for PFS will be presented. A 2-sided 95% confidence interval for median PFS will be provided by using the Brookmeyer-Crowley method. Probabilities of remaining alive and progression free at selected time points may also be presented.

PFS analysis will be repeated for the subset of enrolled Japanese patients and for each of the prognostic factors described in section 4.5.2

Situation	Date of Event or Censoring	Outcome
No adequate baseline disease status assessment	Date of randomization + 1 day	Censored
No adequate post-baseline disease status assessment unless death occurs prior to first scheduled post-baseline assessment	Date of randomization + 1 day	Censored

Table 2: Primary PFS Censoring/Event Rule

No documented progression or death	Date of last adequate disease status assessment	Censored
Documented progression with ≤1 missing scheduled disease status assessment before progression	Date of the earliest assessment that results in a finding of unequivocal progression	Event
Death before progression being documented with ≤1 missing scheduled disease status assessment before death	Date of death	Event
Documented progression or death following a gap between adequate disease status assessments equivalent to 2 missed visits	Date of last adequate disease status assessment before the gap	Censored
New anticancer treatment or procedure started before documented progression or death.	Date of last adequate disease status assessment prior to start of new anticancer therapy	Censored

Note: Disease status assessment includes radiologic documentation (CT, PET/CT, MRI scans) (chest, abdomen and pelvis, others as clinically indicated), bone marrow biopsy/aspirate (may not be required of all patients at all scheduled disease status assessments), and focused physical examination (disease related symptoms, liver and spleen assessment). An adequate baseline disease assessment is any assessment with measurable target lesions from scans. An adequate post-baseline disease status assessment is any disease status assessment for which a disease status of CR, PR, SD or PD is arrived per revised International Working Group (IWG) response criteria for malignant lymphoma².

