2.5.2 Expansion Phase

- TEAEs and changes in laboratory values
- DOR, for those patients with CR or PR, defined as the time from the first documentation of response to the first documentation of PD, as determined by the IRC, or death due to any cause
- PFS, defined as the time from the first dose of study treatment to the first documentation of PD, as determined by the IRC, or death from any cause
- DCR, defined as $CR + PR + SD \ge 8$ weeks, calculated using IRC-determined responses
- OS and deaths
- PK parameters of duvelisib and its metabolites

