3.2 Randomization

In the Dose Optimization Phase only, patients will be randomly assigned on C1D1 to either Cohort 1 or 2 on a 1:1 basis via a computer-generated randomization scheme. No stratification methodology will be employed in this study.

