3.6 Analysis Sets

3.6.1 Dose Optimization Efficacy Set

Dose Optimization Efficacy Set will consist of all patients who 1) receive at least one dose of study drug and 2) complete at least one cycle of treatment and 3) have at least one scan to assess disease response after completion of one cycle of treatment.

Efficacy analyses for the dose optimization phase will be performed using the Dose Optimization Efficacy Set for all primary and secondary efficacy analyses using the response determined by the Investigator. The IRC's determination of disease response will be used in supportive efficacy analyses.

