3.6.2 Modified Intent-to-treat (mITT) Analysis Set

The mITT Population will consist of patients who receive at least one dose of study drug.

Efficacy analyses for the dose expansion phase will be performed using the mITT Analysis Set for all primary and secondary efficacy analyses using the response determined by IRC.

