4.6 Visit Windows

Treatment visits, cycles, and days are pre-defined for this study and are pre-specified on the CRF. In the presentation of study data using Study Day and Cycle Day, the following derivations will be used:

- Day 1 of Study = Date of first dose for a patient
- Study Day = Date Date of first dose + 1, if Date is on or after Date of first dose or Study Day = Date Date of first dose, if Date is before Date of first dose

- Day 1 of Cycle = Date of cycle start, as reported on eCRF (per protocol, Day 1 of Cycle 1 should be Day 1 of Study)
- Cycle Day = Date Date of cycle start in current cycle + 1

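### For Expansion-phase PFS, SAP Table 2 censors at a randomisation date that does not exist and gives one narrow group of early deaths two outcomes

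*SAP*

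**What the plan says.** Table 2 in SAP 5.2.2.3 lists situations, each with a date and an outcome. Four features matter here.

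- Rows 1 and 2 (no adequate baseline assessment; no adequate post-baseline assessment) are both censored one day after randomisation. Row 2 reads "No adequate post-baseline disease status assessment unless death occurs prior to first scheduled post-baseline assessment".
- The death row reads "Death before progression being documented with ≤1 missing scheduled disease status assessment before death" and makes the patient an event on the date of death.
- The gap row censors progression or death after two missed visits. A further row censors at the last adequate assessment before new anticancer therapy.
- The note to the table counts as adequate after baseline "any disease status assessment for which a disease status of CR, PR, SD or PD is arrived", so unscheduled and end-of-treatment scans can qualify.

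Other sections fix who is affected. SAP 3.2 says "In the Dose Optimization Phase only, patients will be randomly assigned on C1D1 to either Cohort 1 or 2 on a 1:1 basis". SAP 2.5.2 gives "PFS, defined as the time from the first dose of study treatment to the first documentation of PD" or death from any cause, and SAP 4.6 adds "Day 1 of Study = Date of first dose for a patient". The Dose Optimization Efficacy Set admits only patients who "have at least one scan to assess disease response after completion of one cycle of treatment", whereas for the Expansion phase "The mITT Population will consist of patients who receive at least one dose of study drug". Protocol 11.9 leaves all censoring rules to the SAP, so there is no fallback.

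**The concern.** Row 2 applies to treated patients with no usable scan after baseline. The Dose Optimization Efficacy Set excludes nearly all such patients, while the Expansion mITT set keeps them. The row therefore falls mainly on patients who have no randomisation date, and a programmer would have to invent one.

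The overlap with the death row matters more. Two programmers following the same SAP could report different PFS for the same early deaths. One reading removes known deaths from an endpoint defined to include death from any cause. SAP 3.5 foresees submission and publication of interim results from this single-arm phase, so the rule should be unambiguous even for a descriptive endpoint.

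**Working it through.** The documents state no PFS event count, rate or power, so there is no plan figure to reproduce. The check is logical first, then a rough sizing.

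**Scan days.** Protocol Table 4 puts the first Expansion scan just before Cycle 3 and the next at Cycle 5 Day 1, with 28-day cycles. Nominal days are 2×28+1 = 57 and 4×28+1 = 113.

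**Applying the rows** to an Expansion patient with no adequate post-baseline assessment of any kind and no new therapy:

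| Day of death | Row 2 | Death row | Result |
|---|---|---|---|
| before 57 | exempt | event (0 missed) | event |
| 57 to 112 | censored at start | event (1 missed) | two outcomes |
| 113 or later | censored at start | does not apply (2 missed) | censored |

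The gap row needs two missed visits, so it does not settle the middle line. A patient with an earlier adequate scan never meets row 2, so a death after one later missed scan is an event only.

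**How many patients.** Let N be the number of patients, u the share with no adequate post-baseline assessment, and m their median time to death in weeks (exponential). Then

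affected = N × u × [2^(−57/7m) − 2^(−113/7m)].

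The bracket is 0.247 for m = 8, 0.231 for m = 12 and 0.206 for m = 16. I assume u = 3% to 15% and m = 8 to 16.

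- N = 100: from 100×0.03×0.206 = 0.6 to 100×0.15×0.247 = 3.7.
- N = 130: 0.8 to 4.8.
- If half of these patients had started new therapy first (an assumption), the range for N = 100 halves to about 0.3 to 1.9.

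The trial's own data do not narrow u. Protocol 1.3 reports no Cohort 2 patient among 11 stopping before the first assessment; the exact 95% upper limit is 1 − 0.025^(1/11) = 28.5%. All six early stops were in Cohort 1, which had a different starting dose.

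**Effect on the curve.** Suppose k patients are affected, there is no other censoring, and x of the other N − k are still event-free.

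- After the affected deaths, PFS is x/(N−k) under row 2 and x/N under the death row. The difference is (row 2 PFS) × k/N, never negative.
- Before the affected deaths, the death row gives (x+k)/N. Row 2 is then lower by (k/N)(1 − x/(N−k)), because those patients are absent from the risk set at the day-57 scan.

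So the upward direction holds once the affected deaths have occurred, that is, from the second scan onward.

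**Simulation.** With N = 100, the u and m above, median PFS of 12 to 26 weeks in scanned patients, and no new therapy before death, PFS just after the day-113 scan averages 0.2 to 2.3 points higher under row 2. Just before that scan it is 0.4 to 2.9 points higher. No simulated trial gave a lower value at either time.

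**Effect on the median**, which is a planned output. In an illustrative set of 100 exponential times with 3 affected deaths, the Kaplan-Meier median moves from 2.96 to 3.04, 3.94 to 4.18 and 5.91 to 6.26 months for assumed medians of 3, 4 and 6 months.

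**Missing date.** Censoring at day 1 or 2 precedes every scan and almost every event, so the choice of date barely moves the curve.

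**The case against.** Row 2 has a natural reading. Its exception for deaths before the first scheduled assessment would do little work if the death row also captured later deaths, so row 2 could be taken as the specific rule that prevails. Making these deaths events is then a change of rule, not a clarification. That is fair as far as it goes. But the SAP does not say that row 2 prevails, and the death row and the endpoint definition point the other way.

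The effect is also limited and partly visible. The end-of-treatment scan and the two-monthly scans after stopping for reasons other than progression reduce the number with no assessment. Patients who start new therapy fall under another row. The SAP reports censored patients by reason, lists best response with a death flag and time to death, and counts every death in OS. PFS at fixed times is only an optional output. All of this stands, and it keeps the point minor.

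A reader might infer two stronger claims. The first is that any death after one missed scan has two outcomes; the table above shows that it needs the first scan to be missed with no adequate post-baseline assessment at all. The second is that the DOR and DOCR rules in SAP 5.2.2.1 are wrong because they do not mention new therapy or missed assessments. Read literally, they give a definite answer: progression or death is the event, and only withdrawal or an ongoing response at the data cut censors. Handling DOR differently from PFS is a design choice, and no bias follows from it.

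**Conclusion.** Both errors in Table 2 are real for the Expansion phase. The randomisation date makes rows 1 and 2 impossible to apply as written, with negligible numerical effect. The overlap gives two outcomes to deaths on nominal days 57 to 112 in patients with no adequate post-baseline assessment and no new therapy.

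The affected group is at most about 0.6 to 3.7 patients per 100, and fewer if some start new therapy first. This rests on an assumed 3% to 15% without an assessment and an assumed median time to death of 8 to 16 weeks. From the second scan onward, censoring these patients can only raise PFS. Between the first scan and the deaths themselves it lowers the curve slightly, so it should not be described as a gain at every time point.

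PFS is secondary and descriptive. ORR and its sample size are untouched. Severity: minor.

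**What to change.** In SAP Table 2:

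1. Rows 1 and 2: replace the date of randomisation with the date of first dose (Day 1).
2. Row 2: reword so that death with no more than one missed scheduled assessment is an event on the date of death, matching the death row.
3. Add one sentence giving the order of precedence among all rows. Changing row 2 alone leaves other overlaps. For example, a patient who starts new therapy on day 40 and dies on day 90 meets both the new-therapy row and the death row. A patient with no adequate baseline who dies early meets both row 1 and the death row.

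The cost is SAP wording and programming, with no new data. Early PFS will be slightly lower than under the row 2 reading once these deaths have occurred.

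Optional clarification, with no error claimed: state in SAP 5.2.2.1 whether new therapy and missed assessments censor DOR and DOCR, and give Kaplan-Meier estimates at 3, 6 and 12 months beside the raw counts. Leave the ORR definition as it is.
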